3.1. Study Rationale

Lung cancer is the leading cause of cancer mortality worldwide, with an estimated rate of 1.8 million new cases per year, and is responsible for the majority of deaths due to cancer (1.59 million) (GLOBOCAN Population Fact Sheets page [WWW]). Small-cell lung cancer (SCLC) is a rapidly growing tumor, with approximately 60% to 70% of patients presenting with metastatic disease at diagnosis that accounts for 12% of new lung cancer cases (Wakuda et al. 2015). Approximately two-thirds of patients with SCLC present with extensive stage disease (ED-SCLC), which has traditionally been defined as disease beyond the ipsilateral hemithorax and may include malignant pleural effusion, pericardial effusion, or hematogenous metastases (Micke et al. 2002).

SCLC is highly sensitive to chemotherapy, with combination chemotherapy remaining the focus of treatment for patients with ED-SCLC. About 60% to 80% of patients with extensive stage disease respond to combination chemotherapy (Hann and Rudin 2008). Cisplatin or carboplatin in combination with etoposide are commonly used regimens in the first-line treatment of SCLC. After an initial response, however, nearly all patients with extensive disease will relapse and the majority of patients will eventually die from their disease (Sundstrom et al. 2002). Platinum-refractory disease shows progression during therapy or within <90 days of the last dose of platinum. Platinum-sensitive disease shows progression ≥ 90 days after the last dose of platinum. Patients with platinum-sensitive disease have a higher likelihood of response to second-line treatment. Their response rate is approximately 20% to 25% (Fruh et al. 2013; Kalemkerian et al. 2013). In contrast, patients with platinum-refractory disease have a $\leq 10\%$ chance of response to a second-line treatment (Kalemkerian et al. 2013). If left untreated, a relapsed patient will typically live 2 months to 4 months (Wakuda et al. 2015).

Several other agents have been shown to have activity in SCLC, and many studies have compared 3-drug regimens to the standard 2-drug regimens with no improvement in efficacy. Topotecan is approved for patients that have ED-SCLC that have failed or relapsed after first line chemotherapy (Demedts et al. 2010). Patients receiving topotecan (1.5 mg/m² daily for 5 days every 21 days) had an overall response rate of 24.3% (von Pawel et al. 1999). The median time to progression was 13.3 weeks and median survival was 25.0 weeks (von Pawel et al. 1999). Adverse events (AEs) associated with this treatment included Grade 4 neutropenia (70.2%), Grade 3/4 anemia (42.3%), Grade 4 thrombocytopenia (28.8%), and documented infection within 2 days of Grade 4 neutropenia (28%) (von Pawel et al. 1999). Other agents, including paclitaxel, irinotecan, vinorelbine, and gemcitabine, have been tested in the second-line setting in an effort to improve on the efficacy and tolerability of topotecan. Despite the modest benefit of topotecan, they have not increased efficacy over topotecan (Chan and Coward 2013), demonstrating the clear need for new agents to improve outcomes for patients with ED-SCLC.

Checkpoint kinase 1 (CHK1), a multifunctional protein kinase, is a regulator of the deoxyribonucleic acid (DNA) damage response (Dai and Grant 2010). CHK1 is a key component of the checkpoint response following DNA damage and is essential for homologous

recombination repair of DNA double strand breaks. It also affects the initiation of DNA replication origin firing, stabilization of replication forks, resolution of replication stress, and coordination of mitosis, even in the absence of exogenous DNA damage (McNeely et al. 2014). Although CHK1 inhibitors previously have been developed as chemopotentiators, given the integral role that CHK1 plays in DNA replication and the regulation of the cell cycle, inhibitors of CHK1 may also have single-agent activity. In particular, replication stress is emerging as a factor that may play a sensitizing role for response to monotherapy with CHK1 inhibitors (Lecona and Fernandez-Capetillo 2014).

SCLC is a tumor associated with replication stress and may be sensitive to the effects of a CHK1 inhibitor (Byers et al. 2012; Thompson et al. 2012). Furthermore, tumors with MYC alterations, which occur in approximately 20% of patients with SCLC (Byers and Rudin 2015), may have increased replication stress and higher sensitivity to CHK1 inhibition (Cole et al. 2011; Høglund et al. 2011). Short hairpin ribonucleic acid (shRNA)-mediated targeted CHK1 knockdown significantly decreased the proliferation of SCLC lines and increased the level of pH2AX, a marker of DNA damage (Sen et al. 2015), providing further evidence that CHK1 may be an attractive target for this disease.

3.2. Background

LY2606368 is an adenosine-5'-triphosphate-competitive inhibitor of CHK1. LY2606368 inhibits the enzymatic activity of CHK1 with a half-maximal inhibitory concentration (IC₅₀) of <1 nM and CHK2 with an IC₅₀ of 8 nM in in vitro assays (King et al. 2015). In nonclinical studies, LY2606368 induced DNA damage as measured by pH2A.X, a marker of double-stranded DNA breaks, and replication catastrophe. LY2606368 inhibited tumor growth in cancer xenografts, including SCLC models, as monotherapy and in combination with other agents (Wu et al. 2012; McNeely et al. 2014; King et al. 2015; Sen et al. 2015). In vitro data from cell viability screens across a large panel of tumor lines representing different tumor histologies demonstrated increased sensitivity to growth inhibition by LY2606368 in SCLC compared to other lung subtypes as well as generally increased sensitivity in tumor cell lines that were MYC amplified (data on file). In a panel of 39 SCLC lines, proteomic analysis revealed that sensitivity to LY2606368 was associated with elevated basal expression of total and phosphor cMYC (p=.01) (Sen et al. 2015).

LY2606368 has been evaluated in human clinical trials as a monotherapy for patients with solid tumors (Study I4D-MC-JTJA [JTJA], NCT01115790) and in combination with either chemotherapy or targeted agents (I4D-MC-JTJF, NCT02124148). In these Phase 1 studies, LY2606368 has shown an acceptable safety/tolerability profile.

3.2.1. Prior Clinical Experience with LY2606368 as a Monotherapy: Study JTJA

LY2606368 was assessed as a monotherapy for patients with solid tumors and demonstrated an acceptable safety/tolerability profile, with transient neutropenia being the primary toxicity.

As of 27 August 2015, data were available from 146 patients who were treated with LY2606368 on Days 1, 2, and 3, or on Day 1 only of a 14-day schedule. The maximum tolerated dose (MTD) of LY2606368 administered on Days 1, 2, and 3 every 14 days was determined to be 40 mg/m², and the MTD of LY2606368 when administered on Day 1 every 14 days was determined to be 105 mg/m². A dose of 105 mg/m² once every 14 days was selected as the recommended Phase 2 dose for monotherapy.

In patients who have received 105 mg/m² of LY2606368, neutropenia was the most frequent and severe toxicity following treatment with LY2606368. Grade 4 decreases in neutrophils deemed related to LY2606368 treatment were observed in 71% of these patients. In general, neutrophil counts nadir on Day 8 and Grade 4 decreases were often less than 5 days. Grade 4 decreases in platelets were observed in 5.7% of patients. Grade 4 anemia was not observed. Nonhematologic toxicity occurred at a lower frequency than hematologic toxicity and was predominantly Grade 1 in severity.

In the 105 patients who received LY2606368 at a dose of 105 mg/m² once every 2 weeks, the treatment-related AEs most frequently reported following LY2606368 treatment in Study JTJA include neutrophil count decreased (93%), platelet count decreased (46%), anemia (33%), white blood cell decreased (30%), fatigue (28%), nausea (14%), febrile neutropenia (11%), and headache (11%).

Please see the Investigator's Brochure (IB) for additional information on the nonclinical and clinical experience with LY2606368.

3.3. Benefit/Risk Assessment

Given the high unmet need for additional therapies for patients with previously treated ED-SCLC, the mechanistic rationale that supports a role for CHK1 inhibition in improving outcomes for patients with SCLC, the nonclinical data with LY2606368 as a monotherapy in nonclinical models (including SCLC), and the clinical safety profile of LY2606368, the risk/benefit assessment supports assessing LY2606368 monotherapy in the proposed patient population.

More information about the known and expected benefits, risks, serious adverse events (SAEs), and reasonably anticipated AEs of LY2606368 are to be found in the IB.

3.4. Rationale for JTJH Amendment (a)

Amendment (a) was developed to address requests resulting from member states participating in the Voluntary Harmonisation Procedure during the assessment of the initial clinical trial application for Study JTJH in the European Union. At the member states' request, the protocol was modified to incorporate those states' recommendations in the inclusion and exclusion

criteria and to establish the actions to be taken in case of prolongation of the QT/QTc interval >480 msec. Because a protocol amendment was required, the opportunity was taken to also include several other minor protocol improvements and clarifications.

4. Objectives and Endpoints

[Table JTJH.4.1](#) shows the objectives and endpoints of the study.

Table JTJH.4.1. Objectives and Endpoints

Objectives	Endpoints
Primary	

 • Cohort 1: To estimate the ORR when a dose of 105 mg/m² LY2606368 every 14 days is administered to patients with ED-SCLC that have platinum-sensitive disease • Cohort 2: To estimate the ORR when a dose of 105 mg/m² LY2606368 every 14 days is administered to in patients with ED-SCLC that have platinum resistant/refractory disease 	
 • Best overall response (PR+CR) as determined per RECIST version 1.1
Secondary	

 • To characterize the safety and toxicity profile of LY2606368 	
 • The safety endpoints evaluated will include but are not limited to the following: AEs, SAEs, clinical laboratory tests, ECGs, vital signs, and physical examinations.

 • To characterize the PK of LY2606368 	
 • LY2606368 concentration in plasma

 • To estimate secondary efficacy measures including DCR, DoR, PFS, and OS 	
 • DCR: best overall response (CR, PR) and SD as determined per RECIST, version 1.1 • DoR: time from the date of an objective response until PD, per RECIST 1.1 or the date of death from any cause in the absence of PD • PFS: time from enrollment until the first radiographic documentation of progression or death from any cause in the absence of PD • OS: time from enrollment until death from any cause

 • To evaluate the association between best tumor response and change from baseline in lung cancer specific-symptoms, symptomatic distress, activity status, overall quality of life, total LCSS score, and ASBI for patients who have platinum-sensitive or platinum resistant/refractory SCLC 	
 • Lung cancer symptoms (appetite loss, fatigue, cough, dyspnea, hemoptysis, and pain), summation items (symptomatic distress, activity level, and global quality of life), total LCSS, and ASBI
Tertiary/Exploratory	

 • To explore biomarkers associated with the efficacy and safety of LY2606368, the exposure (PK) of LY2606368, the mechanism of action of CHK1, DNA damage response pathways or downstream effects, cell cycle markers, immune function, or cancer pathobiology 	
 • Biomarker research on genetic and circulating factors may be assessed from tumor tissue, whole blood, and plasma samples, unless precluded by local regulations.

 • To explore whether ongoing measurement of tumor shrinkage (such as changes in tumor size) correlate with efficacy measures 	
 • Tumor measurements

Abbreviations: AEs = adverse events; ASBI = Average Symptom Burden Index; CHK1 = checkpoint kinase 1; CR = complete response; DCR = disease control rate; DoR = duration of response; ECG = electrocardiogram; ED-SCLC = extensive-stage disease small cell lung cancer; LCSS = Lung Cancer Symptom Scale; ORR = overall response rate; OS = overall survival; PD = progressive disease; PFS = progression-free survival; PK = pharmacokinetics; PR = partial response; RECIST = Response Evaluation Criteria In Solid Tumors; SAEs = severe adverse events; SD = stable disease.

5. Study Design

5.1. Overall Design

Study I4D-MC-JTJH (JTJH) is a multicenter, nonrandomized, parallel-cohort Phase 2 study of LY2606368 in patients with ED-SCLC who have either platinum-sensitive or platinum-resistant/refractory disease.

5.2. Number of Patients

Approximately 116 patients (58 platinum-sensitive patients and 58 platinum-refractory/resistant patients) will be enrolled to receive LY2606368.

5.3. End of Study Definition

End of the study is the date of the last visit or last scheduled procedure for the last patient.

5.4. Scientific Rationale for Study Design

An open-label, single-arm, nonrandomized study without concurrent controls is appropriate for patients with second-line or greater ED-SCLC. There is not currently a uniform standard of treatment for patients with resistant/refractory disease, and clinical trials are recommended (Fruh et al. 2013; Kalemkerian et al. 2013). Historical response rates are reported to be approximately 10%, and so large improvements on these options can be detected using a single-arm design. Although topotecan is the standard for patients with platinum-sensitive disease, the response rates (approximately 20%-25%) are well established from historical controls (von Pawel et al. 1999; Fruh et al. 2013; Kalemkerian et al. 2013).

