6.2. Exclusion Criteria

Patients will be excluded from the study if they meet **any** of the following criteria:

- [10] have received more than 2 prior therapies for ED-SCLC (including immunotherapy, targeted therapies, or chemotherapy)

Each line of therapy is preceded by disease progression. Discontinuation of a regimen without progression (for example, due to toxicity) or a switch of an agent within the same drug class (for example, cisplatin to carboplatin) within a regimen to manage toxicity does not define the start of a new line of therapy. Similarly, maintenance therapy (continuation maintenance or switch maintenance) will not be considered a new line of treatment.

- [11] have symptomatic central nervous system (CNS) malignancy or metastasis. Asymptomatic patients with treated CNS metastases are eligible for this study if they are not currently receiving corticosteroids to treat CNS metastases. CNS metastases should be stable for at least 14 days by clinical assessment, and patients should not have received corticosteroids to treat CNS metastases within 14 days of the first dose of study drug.
- [12] have a second primary malignancy that in the judgment of the investigator and Lilly may affect the interpretation of results
- [13] are currently enrolled in a clinical trial involving an investigational product or any other type of medical research judged not to be scientifically or medically compatible with this study
- [14] have previously completed or withdrawn from this study or any other study investigating LY2606368 or a CHK1 inhibitor or have shown hypersensitivity to any of the components of the LY2606368 formulation
- [15] have a known serious concomitant systemic disorder (for example, active infection or cardiac disease) that, in the opinion of the investigator, would compromise the patient's ability to adhere to the protocol
- [16] have a symptomatic human immunodeficiency virus (HIV) infection or symptomatic activated/reactivated hepatitis A, B, or C (screening is not required). If the medical history, symptoms, and/or laboratory values suggest that the patient may have HIV or hepatitis A, B, or C, appropriate assessment should be conducted to determine whether the patient should be excluded.
- [17] have a serious cardiac condition, such as:
- symptomatic congestive heart failure
 - New York Heart Association Class III/IV heart disease
 - unstable angina pectoris
 - symptomatic or poorly controlled cardiac arrhythmia

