10.1. Sample Size Determination

The study will enroll approximately 116 patients (58 platinum-sensitive patients, 58 platinum-refractory/resistant patients).

For the platinum-sensitive cohort, it is assumed that a true overall response rate (ORR) of less than 20% indicates inadequate antitumor activity. Given that a futility interim analysis will be conducted on the first 29 patients' response data, then with a one-sided significance level of 0.1, a sample size of 58 patients will provide approximately 90% power to detect a true ORR of at least 35%, i.e. 16 or more confirmed overall responses (complete response [CR] or partial response [PR]) are observed in all 58 patients.

For the platinum-refractory/resistant cohort, it is assumed that a true ORR of less than 5% indicates inadequate anti-tumor activity. Given that a futility interim analysis will be conducted on the first 29 patients' response data, then with a one-sided significance level of 0.1, a sample size of 58 patients will provide approximately 90% power to detect a true ORR of at least 15%, i.e. 6 or more confirmed overall responses (CR or PR) are observed in all 58 patients.

For each cohort, the overall type II error rate, i.e. the probability of terminating an effective cohort, will be controlled using a Lan-DeMets spending function (Lan and DeMets 1983), which generates boundaries that are very similar, though not identical, to the classical stopping boundaries of O'Brien and Fleming (1979). The type II error rate spent at interim analysis after the first 29 patients for each cohort is approximately 2%; the cumulative type II error rates spent at final analysis for platinum-sensitive cohort and platinum-refractory/resistant cohort are 9.9% and 9.4%, respectively.

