10.3.1. Efficacy Analyses

Overall response rate (ORR) is defined as the number of patients who achieve a best overall response of CR or PR, divided by the total number of patients enrolled to the corresponding cohort (ITT population). Complete or partial responses may be claimed only if the criteria for each are met at a subsequent time point (greater than 4 weeks). The ORR, with 95% and 80% CIs, will be summarized for each cohort using the Clopper-Pearson method.

Disease control rate (DCR) is defined as the number of patients who achieve a best overall response of CR, PR, or stable disease (SD) divided by the total number of patients enrolled to the corresponding cohort (ITT population). The confirmation of CR and PR is required. In the case of SD, measurements must have met the SD criteria at least once after study entry at a minimum interval (in general not less than 6 weeks). The DCR, with 95% CI, will be summarized for each cohort using the Clopper-Pearson method.

Duration of response is defined as the time from the date measurement criteria for CR or PR (whichever is first recorded) are first met until the first date that disease is recurrent or objective progression is observed, per RECIST 1.1 criteria, or the date of death from any cause in the absence of objectively determined disease progression or recurrence.

Overall survival is defined as the time from enrollment until death from any cause. If the patient is alive or lost to follow-up at the time of data analysis, OS data will be censored on the last date the patient is known to be alive. Overall survival curves, the median and survival rates at various time points with 95% CI, for each cohort will be estimated using the Kaplan-Meier method (Kaplan and Meier 1958).

Progression-free survival is defined as the time from enrollment until the first radiographic documentation of progression or death from any cause in the absence of PD. Patients known to be alive and without disease progression will be censored at the time of the last adequate tumor assessment prior to study completion (a detailed PFS event/censoring scheme is provided in SAP). Progression-free survival curves, median PFS, and PFS rates at various time points with

95% CI for each cohort will be estimated using the Kaplan-Meier method (Kaplan and Meier 1958).

Exploratory sensitivity analyses on efficacy endpoints may be conducted as described in the SAP.

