10.3.4. Interim Analyses

For each cohort, one interim analysis of futility will be conducted after the 29th patient in the cohort has completed Cycle 3, and, if required, the response is confirmed. The interim analysis will be conducted to assess whether the respective cohort is unlikely to achieve statistical

significance on its primary endpoint and may also include PK data in order to confirm that patients are in the expected exposure range.

The stopping rule for interim analysis is defined as follows:

- Platinum-sensitive cohort:
 - If 4 or fewer confirmed overall responses (CR or PR) are observed in the first 29 patients, then the cohort will be terminated; otherwise, the cohort will continue.
- Platinum-refractory/resistant cohort:
 - If 0 confirmed overall responses (CR or PR) are observed in the first 29 patients, then the cohort will be terminated; otherwise, the cohort will continue.

11. References

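### Does Cohort 2's test against 5% undercut a single-arm design that is justified by a historical response rate of about 10%?

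*Protocol*

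**What the plan says.** Protocol 5.4 explains why resistant/refractory disease can be studied without a concurrent control: "Historical response rates are reported to be approximately 10%, and so large improvements on these options can be detected using a single-arm design". Protocol 3.1 gives the same figure as an upper limit; there, 10% or less is the "chance of response to a second-line treatment". Cohort 2 is not purely second-line, since Protocol 6.2 excludes only patients who "have received more than 2 prior therapies for ED-SCLC".

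The test uses a different number. In Protocol 10.1, "it is assumed that a true ORR of less than 5% indicates inadequate anti-tumor activity", and the cohort is powered at about 90% for a true ORR of 15%, one-sided alpha 0.1. The interim rule in 10.3.4 is: "If 0 confirmed overall responses (CR or PR) are observed in the first 29 patients, then the cohort will be terminated". The final rule is at least 6 of 58, and SAP 5.1 reads meeting it as an ORR significantly above 5%.

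On estimation, Protocol 10.3.1 states: "The ORR, with 95% and 80% CIs, will be summarized for each cohort using the Clopper-Pearson method". SAP 5.10.1 plans the same. Neither names a value to compare the intervals with. The primary objective in both documents is to estimate the ORR in each cohort.

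For Cohort 1, Protocol 5.4 says that "the response rates (approximately 20%-25%) are well established from historical controls", Protocol 3.1 cites 24.3% for topotecan, and the final rule of at least 16 of 58 is read against 20%.

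**The concern.** An uncontrolled trial has only the historical rate to set its result against. Section 5.4 puts that rate at about 10%, while the success rule tests half of it. A drug no better than the cited rate would meet the rule about as often as not, and the smallest passing estimate, 6/58 = 10.3%, practically equals the benchmark.

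If nothing says in advance how the result is to be read against 10%, the question of whether the trial showed the improvement that justified its design could be settled after the data are in. This would not be a rare situation: at the planned ORR of 15%, the cohort ends with 6 to 9 responses about half the time, and for all of these counts the 80% interval still includes 10%.

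Cohort 1 looks similar in milder form, because 20% is the low end of its cited 20% to 25% range.

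**Working it through.** **Inputs.** Cohort 2: interim at 29 patients, stop at 0 responses (Protocol 10.3.4); final n = 58, success at 6 or more, floor 5%, target 15%, one-sided alpha 0.1 (Protocol 10.1, SAP 5.1); benchmark about 10% (Protocol 5.4) or at most 10% (3.1). True rates of 6% to 8%, and of 20% and above, are assumptions made to show the range.

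**Formula.** With X1 ~ Bin(29, p) and an independent X2 ~ Bin(29, p),

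P(success; r, p) = sum over x = 1 to 29 of P(X1 = x) × P(X2 ≥ r − x).

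The term x = 0 is left out because the cohort stops there. Its probability is (1 − p)^29: 22.6% at 5%, 4.7% at 10% and 0.9% at 15%.

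**The plan's own figures first (r = 6).** At p = 5% the attained one-sided error is 0.0685, within 0.1. A cutoff of 5 would give 0.1605, so 6 is the smallest cutoff that meets alpha. At p = 15% the power is 0.8826, which fits the stated approximately 90%. The exact type II error is therefore 11.7%, against the stated cumulative 9.4%; this does not bear on the present question.

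**Chance of meeting 6/58 at other rates:**

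| True ORR | 5% | 6% | 7% | 8% | 10% | 15% |
|---|---|---|---|---|---|---|
| P(≥6/58) | 6.8% | 13.2% | 21.7% | 31.6% | 52.6% | 88.3% |

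**Planned intervals.** The Clopper-Pearson lower limit is the a-quantile of Beta(x, 59 − x) and the upper limit is the (1 − a)-quantile of Beta(x + 1, 58 − x), with a = 0.10 for 80% and a = 0.025 for 95%.

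| Responses | Estimate | 80% interval | 95% interval |
|---|---|---|---|
| 6/58 | 10.3% | 5.5% to 17.5% | 3.9% to 21.2% |
| 9/58 | 15.5% | 9.6% to 23.4% | 7.4% to 27.4% |
| 10/58 | 17.2% | 11.0% to 25.3% | 8.6% to 29.4% |
| 11/58 | 19.0% | 12.4% to 27.2% | 9.9% to 31.4% |
| 12/58 | 20.7% | 13.9% to 29.1% | 11.2% to 33.4% |

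The lower limit first exceeds 10% at 10/58 for the 80% interval and at 12/58 for the 95% interval.

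**What a threshold of 10/58 would do (0/29 stop kept):**

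| True ORR | 10% | 15% | 20% | 25% | 30% |
|---|---|---|---|---|---|
| P(≥10/58) | 6.0% | 36.9% | 74.9% | 94.0% | 99.1% |

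At 15%, P(6 to 9 responses) = 0.8826 − 0.3694 = 0.5132, about 51%. A drug at the planned rate would miss the threshold with probability 1 − 0.3694 = 63%.

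**Cohort 1 (stop at 4 or fewer of 29).** P(≥16/58) is 32.3% at 24.3% and 36.9% at 25%. The 80% lower limit first exceeds 24.3% at 19/58 (24.6%) and 25% at 20/58 (26.2%). At 20/58 the 95% lower limit is 22.5%.

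**The case for a change.** The strongest case for a change is this. Section 5.4 draws its permission to run without a control from 10%, the documents never say why 5% is then the floor, and a one-sentence reading of an interval that is already planned would cost no patients and no extra analysis. Estimation as the objective does not answer this fully, because SAP 5.1 also sets a significance rule, and sets it at 5% only.

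The mismatch stands, and so does the arithmetic. The inference from it is weaker, for four reasons.

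- The 53% is not an error rate of the stated test, which is against 5%. It depends on placing the benchmark at exactly 10%. Section 3.1 gives 10% as a ceiling for second-line treatment, and the cohort also admits patients with two prior therapies. At an assumed 7% to 8% the figure falls to 22% to 32%.
- The overclaim to be prevented appears nowhere in the plan. No section promises a statement of superiority over historical treatment.
- A threshold at 10/58 relies on the 80% interval, although both documents use 95% by default and plan both for ORR. At 10/58 the 95% interval still reaches down to 8.6%, so a declared improvement would stand beside a reported interval that includes the benchmark.
- For Cohort 1, 5.4 claims only that historical rates are well established, not that large improvements will be detected. The tested 20% lies within the cited range, and choosing between 19 and 20 responses has no basis in the documents.

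**Conclusion.** The gap between the 10% rationale and the 5% floor is real and unexplained, but it is a matter of interpretation that analysts can handle from the planned output. The Cohort 2 rule does what SAP 5.1 says of it: it shows activity above 5%, with an attained one-sided error of 6.8%. Its conclusion is limited to that, and the exact 80% and 95% intervals will be printed beside the estimate. A result of 6 to 9 responses will therefore show on its face that 10% has not been excluded.

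Section 5.4 is also not contradicted. It speaks of large improvements, and 58 patients can separate these from 10%: 94% at a true ORR of 25% and 99% at 30% under the stricter 80% reading. At 20% the figure is 75%, so that rate should not be called reliably detectable.

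A fixed threshold would cut the chance of an improvement statement at a true 10% from 53% to 6%, but would fail a drug at the planned 15% in 63% of trials, measured against an approximate benchmark. That is a trade-off and not a correction. Sample size, futility stops and both final rules can stay as written.

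This conclusion assumes that the report keeps to the wording of SAP 5.1 and does not present a bare 6/58 as an improvement over about 10%.
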